### 9.7.1.8.3 Laboratory Values

For all quantitative parameters listed in Section 9.5.1.3.3, the actual value and the change at the 18th week from baseline will be summarized using descriptive statistics. Qualitative parameters listed in Section 9.5.1.3.3 will be summarized using frequencies (number and percentage of subjects), and changes at the 18th week from baseline will be reported using shift tables. Percentages will be based on the number of subjects with both non-missing baseline and 18 weeks results.

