##### **9.5.1.3.1 Adverse Events**

Adverse Event (AE) refers to an unfavorable and unintended sign (e.g. abnormal laboratory finding) associated with administration/use of study drug, symptom, or disease, whether or not related to the medicinal (investigational) product. For this study, the study drug is safinamide mesilate.

The criteria for identifying AEs in this study are:

- Any unfavorable and unintended sign (including an abnormal laboratory finding), symptom, or disease temporally associated with the use of an investigational product, whether or not considered related to the investigational product (Note: Every sign or symptom should not be listed as a separate AE if the applicable disease [diagnosis] is being reported as an AE)
- Any new disease or exacerbation of an existing disease.
- Any deterioration in nonprotocol-required measurements of a laboratory value or other clinical test (e.g., ECG or x-ray) that results in symptoms, a change in treatment, or discontinuation of study drug.
- Recurrence of an intermittent medical condition (e.g., headache) not present pretreatment (baseline).
- An abnormal laboratory test result should be considered an AE if the identified laboratory abnormality leads to any type of intervention, withdrawal of study drug, or withholding of study drug, whether prescribed in the protocol or not.

All AEs, regardless of relationship to study drug or procedure, should be recorded beginning after Visit 1 (Screening) through the last visit. Refer to Section 9.5.4.1 for the time period after the end of treatment for SAE collection.

Abnormal laboratory values should not be listed as separate AEs if they are considered to be part of the clinical syndrome that is being reported as an AE. It is the responsibility of the investigators to review all laboratory findings in all subjects and determine if they constitute an AE. Medical and scientific judgment should be exercised in deciding whether an isolated laboratory abnormality should be classified as an AE. Any laboratory abnormality considered to constitute an AE should be reported on the Adverse Event CRF.

All AEs must be followed until the end of the study (subject's last visit). All Serious Adverse Events (SAEs) must be followed to resolution or, if resolution is unlikely, to stabilization.

**Every effort must be made by the investigators to categorize each AE according to its severity and its relationship to the study drug.**

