- c A subject who prematurely discontinues taking the study drug should return to the site as soon as practicable after discontinuing study drug (preferably within 7 days) to complete Premature Discontinuation Visit. Following the completion of Premature Discontinuation Visit, the subjects who require taper will undergo a Taper Period for 1 week
- d Demography information includes year and month of birth (age) and sex
- e All medical history within 6 months and surgical history within 3 years will be recorded in the medical history CRF
- f Prior medication within 1 month and current medications (including levodopa) will be recorded at Visit 1 (Screening).  
The information on prior medication will include the name of the product or ingredient, dose and administration (daily dose and dose unit), administration period (start date and end date), and purpose of administration

- Any concomitant medications and therapies during this study (starting at the date of informed consent) will be recorded at each visit. The information on concomitant medications (including levodopa) will include the name of product or ingredient, dose and administration (daily dose and dose unit), administration period (start date and end date), and purpose of administration. The information on concomitant therapies should include the name of therapy, therapy period (start date and end date), and purpose of therapy. Any Adverse Events or medical status shall be recorded during the administration of concomitant medication or use of concomitant therapy.
- g Clinical laboratory tests to be performed according to the guideline of each site
- At Visit 3 and Visit 5, clinical laboratory tests will only be performed if considered necessary by an investigator based on the subject's symptoms
- In case of tests related to liver function, a re-test or re-screening is allowed once during the Screening period
- h ECG will only be performed if considered necessary by an investigator based on the subject's symptoms
- i Vital signs will include blood pressure, pulse, and body temperature. Vital signs will be measured preferably after the subject has rested comfortably for 5 minutes at each visit
- j Females of childbearing potential only. A dipstick will be used for urine pregnancy testing
- k Subjects will administer the study drug at the dose prescribed at regular visits from the next day after that visit to the day of the next regular visit

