#### **9.5.5 Completion/Discontinuation of Subjects**

In this study, subjects are assumed to have completed the clinical trial upon their completion of Visit 4 (EOT).

A subject may elect to discontinue the study at any time for any reason. All subjects who discontinue the study are to complete the study's early discontinuation procedures indicated in Table 3.

An investigator will promptly explain to the subject involved that the study will be discontinued for that subject and provide appropriate medical treatment and other necessary measures for the subject. A subject who has ceased to return for visits will be followed up by mail, phone, or other means to gather information such as the reason for failure to return, the status of treatment compliance, the presence or absence of AEs, and clinical courses of signs and symptoms.

Subjects who discontinue early from the study will be discontinued for the following reasons: AE, lost to follow-up, withdrawal of consent by subject, lack of efficacy, noncompliance with study procedure, impossibility to increase study drug dose, pregnancy, study terminated by sponsor, or other.

A subject removed from the study for any reason may not be replaced.

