#### **9.7.1.8 SAFETY ANALYSES**

All safety analyses will be performed on the SAS. Safety data will be summarized using descriptive statistics (e.g., n, mean, standard deviation, median, minimum, maximum for continuous variables; n [%] for categorical variables). Safety variables include Treatment-Emergent Adverse Events (TEAEs), clinical laboratory parameters, and vital signs.

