##### **9.7.1.8.2 Adverse Events**

The AE verbatim descriptions (investigator terms from the CRF) will be classified into standardized medical terminology using the Medical Dictionary for Regulatory Activities

(MedDRA). AEs will be coded to the MedDRA (Version 23.0 or higher) Lower Level Term (LLT) closest to the verbatim term. The linked MedDRA PT and primary SOC are also captured in the database.

A TEAE is defined as an AE that emerges during treatment, having been absent at pretreatment (Baseline) or

- Reemerges during treatment, having been present at pretreatment (Baseline) but stopped before treatment, or
- Worsens in severity during treatment relative to the pretreatment state, when the AE is continuous.

Only those AEs that are treatment-emergent will be included in summary tables. All AEs, treatment-emergent or otherwise, will be presented in subject data listings.

The incidence of TEAEs will be reported as the number (percentage) of subjects with TEAEs by SOC and PT. A subject will be counted only once within SOC and PT, even if the subject experienced more than 1 TEAE within a specific SOC and PT. The number (percentage) of subjects with TEAEs will also be summarized by maximum severity (mild, moderate, or severe).

The number (percentage) of subjects with TEAEs will also be summarized by relationship to study drug (Yes [related] and No [not related]).

The number (percentage) of subjects with treatment-related TEAEs will be summarized by SOC and PT. Treatment-related TEAEs include those events considered by the investigators to be related to the study drug. The number (percentage) of subjects with treatment-related TEAEs will also be summarized by maximum severity (mild, moderate, or severe).

AEs will be summarized using the SAS. The number of AEs and number and incidence (%) of subjects with AEs will be summarized by dose level and overall. To obtain the incidence (%), the number of subjects with at least 1 event and the percentage of subjects with AEs by SOC and PT will be calculated. Incidence (%) by causal relationship with study drug and by severity will also be calculated. For clinically significant events, time of onset, and recovery will be reported.

The number (percentage) of subjects with TEAEs leading to death will be summarized by MedDRA SOC and PT. A subject data listing of all AEs leading to death will be provided.

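### Laboratory change and shift tables are fixed at week 18, and no stated rule brings in results from the Premature Discontinuation Visit

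*Combined protocol and SAP*

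**What the plan says.** Section 9.7.1.8.3 sets the time point for the quantitative parameters: "For all quantitative parameters listed in Section 9.5.1.3.3, the actual value and the change at the 18th week from baseline will be summarized". For the qualitative parameters it plans frequencies, and shift tables for the change at week 18. The denominator rule is: "Percentages will be based on the number of subjects with both non-missing baseline and 18 weeks results".

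Section 9.7.1.8 names the population: "All safety analyses will be performed on the SAS". Under Section 9.7.1.2 one dose and one post-dose safety assessment are enough to enter that set, so it can include people who stop early.

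Table 3 gives the Premature Discontinuation Visit its own column, apart from Visit 4, with an unbracketed mark for laboratory tests. Section 9.5.5 makes those procedures apply generally: "All subjects who discontinue the study are to complete the study's early discontinuation procedures indicated in Table 3". Footnote c of Table 3 sets the timing: a subject who stops "should return to the site as soon as practicable after discontinuing study drug (preferably within 7 days) to complete Premature Discontinuation Visit". Footnote g limits the other post-baseline samples: "At Visit 3 and Visit 5, clinical laboratory tests will only be performed if considered necessary by an investigator based on the subject's symptoms".

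Sections 9.7 and 9.7.1 leave further detail to a separate SAP, whose text is not among the documents supplied.

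**The concern.** After screening, the only unconditional laboratory samples in Table 3 are those at Visit 4 and at the Premature Discontinuation Visit. For an early stopper, the discontinuation sample may be the only post-baseline laboratory result. The plan collects it and then gives no rule that places it in the change summary or the shift table.

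Early stopping need not be unrelated to tolerability or to the laboratory values themselves. Section 9.1.3 removes subjects who cannot reach 100 mg/day within 4 weeks. Section 9.4.1 ties termination of study drug to a hepatic score that uses bilirubin and albumin, both in the chemistry panel. A table restricted to people with a week-18 sample may therefore not represent everyone treated. At stake is whether the laboratory tables describe the safety population or mainly the subjects who stayed to the end.

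**Working it through.** **Step 1. Reproduce the plan's own figures.** Inputs from Section 9.7.2: PDQ-39 mean change -3.17, SD 10.86, power 90%, alpha 0.025, drop-out 25%. Section 9.7.1 says the tests are two-sided. A paired t-test with the noncentral t distribution gives n = 149 (power 0.902). Inflation gives 149 / (1 - 0.25) = 198.7, rounded up to 199. Both figures reproduce.

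**Step 2. Count the subjects outside the week-18 tables.** 199 x 0.25 = 49.75, about 50, which agrees with 199 - 149 = 50. At an assumed 10% drop-out, 199 x 0.10 = 19.9, about 20, leaving 179.

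For discontinuation results that go unused, these counts are upper bounds:
- some stoppers will give no sample;
- some may not qualify for the safety set;
- a sample in weeks 16 to 20 (Visit 4 is week 18 plus or minus 2) might be counted as week 18;
- Section 9.5.1.3.3 leaves testing to each site's guideline.

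**Step 3. Count what a last-value table would add.** The share of early stoppers who give a sample is not in the documents, so I assume 50%, 80% and 100%.

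| Drop-out | Week-18 n | Added | New n | Share added |
|---|---|---|---|---|
| 25% | 149 | 25 / 40 / 50 | 174 / 189 / 199 | 14.4% / 21.2% / 25.1% |
| 10% | 179 | 10 / 16 / 20 | 189 / 195 / 199 | 5.3% / 8.2% / 10.1% |

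**Step 4. Effect on a table entry.** Change in the entry = share added x (stoppers minus completers). All the differences below are assumed.

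Percentages, for differences of -2, +5 and +10 points:
- 25 added: 14.4% x (-2, 5, 10) = -0.3, +0.7, +1.4 points.
- 50 added: 25.1% x (-2, 5, 10) = -0.5, +1.3, +2.5 points.
- At 10% drop-out, a difference of +10 points gives 5.3% x 10 = 0.5 to 10.1% x 10 = 1.0 points.

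Mean changes, for differences of -0.2, +0.2 and +0.5 SD:
- 25 added: 14.4% x (-0.2, 0.2, 0.5) = -0.03, +0.03, +0.07 SD.
- 50 added: 25.1% x (-0.2, 0.2, 0.5) = -0.05, +0.05, +0.13 SD.
- At 10% drop-out, a difference of +0.5 SD gives 0.03 to 0.05 SD.

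For scale, the standard error of a mean is 1/sqrt(149) = 0.082 SD with 149 subjects and 1/sqrt(179) = 0.075 SD with 179. If stoppers and completers do not differ, nothing changes.

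**Step 5. Reach of the percentage rule.** Section 9.5.1.3.3 lists 11 haematology, 15 chemistry and 9 urinalysis items, 35 in all. On my reading at most the 9 urinalysis items are qualitative, so the percentage rule and the shift tables cover at most 9 of 35. For the other 26 or more, the restriction comes from the week-18 wording of the change summary.

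**The case against.** The exclusion is inferred. No section says that discontinuation results are left out, and the SAP may bring them in. This stands as a limit on the wording: what can be said is that no supplied rule includes them. The week-18 restriction itself is written down, however, so the SAP would have to add to it.

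The clinically important results have another route. Section 9.5.1.3.1 says: "It is the responsibility of the investigators to review all laboratory findings in all subjects and determine if they constitute an AE". Abnormalities judged to be adverse events go on the adverse event form, and Section 9.7.1.8.2 tabulates the treatment-emergent ones ("Only those AEs that are treatment-emergent will be included in summary tables") and lists all of them. It also tabulates those leading to discontinuation of study drug. This largely stands. It does not cover changes that nobody judged to be an adverse event, and those are what a change or shift table is meant to show.

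A reader might infer that discontinuation results are absent from every laboratory summary. The documents do not support that. In Section 9.7.1.8.3 the actual-value summary and the qualitative frequencies are not clearly tied to week 18 and may include them.

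A reader might also infer a contradiction with the safety population. That does not follow either: the safety set defines who is eligible, and requiring a pair of results for a change or a shift is ordinary practice.

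Finally, a last-value table mixes week-18 samples taken on drug with earlier samples taken after stopping, and there is no comparator arm. That is a fair criticism, and it is why the table should supplement the week-18 tables and be labelled with care.

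**Conclusion.** The point holds for two summaries only: the quantitative change from baseline and the qualitative shift table. Followed as written, they describe essentially completers, while a laboratory sample scheduled for early stoppers has no stated place in them. At the planned 25% drop-out this concerns up to about 50 of 199 subjects; at an assumed 10%, up to about 20.

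Under the assumed differences, the largest effects are 2.5 percentage points and 0.13 SD, the latter about one and a half standard errors (0.126 / 0.082). They require 25% drop-out, a usable pair of results from every stopper, and the largest differences tried. At 10% drop-out the largest effect on a mean, 0.05 SD, is below one standard error. The true size and direction are unknown.

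A reader might conclude that the tables understate laboratory toxicity or hide abnormalities. The documents give no evidence for a direction, and events judged adverse are reported elsewhere. This is a modest gap in the safety reporting that is cheap to close.

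**What to change.** Keep the week-18 tables. In Section 9.7.1.8.3 or the SAP, before database lock:

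- Add one change summary (quantitative parameters) and one shift table (qualitative parameters) from baseline to the last scheduled value: Visit 4 or, if that is absent, the Premature Discontinuation Visit.
- Include all safety-set subjects who have both results, and state how many contribute.
- Label the output *last value through EOT/Premature Discontinuation Visit*. Do not call it on-treatment, because the discontinuation samples follow the stopping of study drug.
- Report days since last dose for the discontinuation samples.

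The cost is some programming and one more set of tables, which must be read knowing that it combines on-drug and post-stopping samples. No new visits or samples are needed: the discontinuation tests are already scheduled, and the last-dose date is needed anyway for duration of exposure in Section 9.7.1.8.1.

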### 9.7.1.8.4 Vital Signs and Weight

Descriptive statistics for the vital sign parameters (systolic and diastolic blood pressure, pulse, body temperature) and weight will be presented by each visit.

### 9.7.1.9 Other Analyses

Levodopa dose administered during the study will be summarized using descriptive statistics (e.g., n, mean, standard deviation, median, minimum, maximum for continuous variables; n [%] for categorical variables). Efficacy analyses will be performed in subgroups based on levodopa dose, and details will be described in the SAP.

## 9.7.2 Determination of Sample Size

The sample size is calculated under assumption the efficacy of this study at 18 weeks is comparable to the efficacy of phase 3 clinical study at 24 weeks.

The sample size is calculated using each 2 primary endpoints, and a larger sample size is selected conservatively. The sample size for each evaluation variable is as follows.

#### 1) Endpoint 1: Paired t-test for “off” time

Based on the above assumptions, to calculate the number of subjects for the comparison of the “off” time mean change 24 weeks after Baseline, the sample size was calculated assuming average change (-1.56) and standard deviation (2.35).

The results were performed through PASS (version 2020), the sample sizes of 31 achieve 90% power and the significance level (alpha) is 0.025.

#### 2) Endpoint 2: Paired t-test for PDQ-39 score

Based on the above assumptions, to calculate the number of subjects for the comparison of the PDQ-39 score mean change 24 weeks after Baseline, the sample size was calculated assuming average change (-3.17) and standard deviation (10.86).

The results were performed through PASS (version 2020), the sample sizes of 149 achieve 90% power, and the significance level (alpha) is 0.025.

According to the above two endpoints, the sample sizes are 31, 149 at each assumption. The sample size of endpoint 2 is larger than endpoint 1. Therefore, the final sample size obtained, considering the drop-out rate of 25% during the study period is 199.

### **9.7.3 Interim Analysis**

No interim analysis is planned for this study.

## **11 PROCEDURES AND INSTRUCTIONS (ADMINISTRATIVE PROCEDURES)**

### **11.1 Changes to the Protocol**

Any change to the protocol requires a written protocol amendment or administrative change that must be approved by the sponsor before implementation. These requirements should in no way prevent any immediate action from being taken by the investigators, or by the sponsor, in the interest of preserving the safety of all subjects included in the study. If the investigators determine that an immediate change to or deviation from the protocol is necessary for safety reasons to eliminate an immediate hazard to the subjects, the sponsor's representative or appropriate study team member and the IRB/IEC for the site must be notified immediately.

### **11.2 Adherence to the Protocol**

The investigators will conduct the study in strict accordance with the protocol (refer to ICH E6, Section 4.5, and KGCP).

### **11.3 Monitoring Procedures**

The CRO's CRA will maintain contact with the investigators and designated staff by telephone, letter, or email between study visits. Monitoring visits to each site will be conducted by the assigned CRA as described in the monitoring plan. The investigators will allow the CRA to inspect the clinical, laboratory, and pharmacy facilities to assure compliance with GCP and local regulatory requirements. The CRFs and subject's corresponding original medical records (source documents) are to be fully available for review by the sponsor's representatives at regular intervals. These reviews verify adherence to study protocol and data accuracy in accordance with local regulations. All records at the site are subject to inspection by the local auditing agency and to IRB/IEC review.

In accordance with ICH E6, Section 1.52, source documents may include, but are not limited to, the following:

- Clinic, office, or hospital charts
- Copies or transcribed health care provider notes that have been certified for accuracy after production
- Recorded data from automated instruments such as IxRS, x-rays, and other imaging reports regardless of how these images are stored, including microfiche and photographic negatives
- Subject diary, PDQ-39, MMSE, MDS-UPDRS Part 3 and Part 4, and KPPS completed by the subjects or investigators
- Records of telephone contacts
- Drug distribution and accountability logs maintained in pharmacies or by research personnel
- Laboratory results and other laboratory test outputs

- Correspondence regarding a study subject's treatment between physicians or memoranda sent to the IRBs/IECs

#### **11.4 Recording of Data**

A CRF is required and must be completed for each subject by qualified and authorized personnel. All data on the CRF must reflect the corresponding source document, except when a section of the CRF itself is used as the source document. Any correction to entries made on the CRF must be documented in a valid audit trail where the correction is dated, the individual making the correction is identified, the reason for the change is stated, and the original data are not obscured. Only data required by the protocol for the purposes of the study should be collected.

The investigators must sign each CRF. The investigators will report the CRFs to the sponsor and retain a copy of the CRFs.

#### **11.5 Identification of Source Data**

All data to be recorded on the CRF must reflect the corresponding source documents.

